	Investigators and sites are listed in the "List of Investigators and Centers Involved in the Trial" document.		
Planned Trial Period:	1Q 2018 to 4Q 2018		
A Phase III, open-label, multi-center study to describe the immune persistence of the priming dose and describe the immunogenicity a of a booster dose of MenACYW conjugate vaccine in children in F who had been vaccinated 3 years earlier as toddlers with either Me conjugate vaccine or Nimenrix® as part of the MET54 study.			
	Subjects who were vaccinated 3 years (± 45 days) earlier at 12 to 23 months of age in study MET54 will be eligible for enrollment in study MET62.		
	All subjects will receive a single dose of MenACYW conjugate vaccine on Day (D) 0.		
	All subjects will provide blood samples for immunogenicity assessment at baseline (pre-vaccination) and at 30 to 44 days after vaccination.		
	Solicited adverse event (AE) information will be collected for 7 days after vaccination; unsolicited AE information will be collected from Visit 1 (D0) to Visit 2 (D30 [+14 days]), and serious adverse event (SAE) information (including adverse events of special interest [AESIs]) will be collected throughout the study period.		
Objectives:	Immunogenicity		
	 To describe the antibody persistence of meningococcal serogroups A, C, Y, and W before a booster dose in children who received either MenACYW conjugate vaccine or Nimenrix[®] 3 years earlier as toddlers To describe the antibody responses to meningococcal serogroups A, C, Y, and W 30 days after a booster dose of MenACYW conjugate vaccine in children who received either MenACYW conjugate vaccine 		
	or Nimenrix® 3 years earlier as toddlers		

	3) To describe the antibody responses against tetanus toxoid 30 days after a booster dose of MenACYW conjugate vaccine in children who received either MenACYW conjugate vaccine or Nimenrix® 3 years earlier as toddlers	
	Safety	
	To describe the safety profile of a booster dose of MenACYW conjugate vaccine in children who received either MenACYW conjugate vaccine or Nimenrix® 3 years earlier as toddlers	
Endpoints:	Immunogenicity	
	 Antibody titers against meningococcal serogroups A, C, Y, and W measured by hSBA and rSBA: 	
	 a) At D0 (baseline) and D30 in toddlers after having received a single dose of either MenACYW conjugate vaccine or Nimenrix[®], as part of study MET54 	
	b) At D0 (baseline) in children before receiving a booster dose of MenACYW conjugate vaccine as part of study MET62 (3 years after having received a single dose of either MenACYW conjugate vaccine or Nimenrix®)	
	2) Antibody titers against meningococcal serogroups A, C, Y, and W measured by hSBA and rSBA at D0 (baseline) and D30 after the administration of a booster dose of MenACYW conjugate vaccine in children who received either MenACYW conjugate vaccine or Nimenrix® 3 years earlier as toddlers	
	Tetanus toxoid is contained as a carrier protein in both the investigational vaccine and the control vaccine that was used in study MET54. Therefore, blood samples will also be tested to assess:	
	3) Antibody concentrations against tetanus toxoid at D0 (baseline) and D30 after the administration of a booster dose of MenACYW conjugate vaccine in children who received either MenACYW conjugate vaccine or Nimenrix® 3 years earlier as toddlers	
	Safety	
	 Occurrence, nature (Medical Dictionary for Regulatory Activities [MedDRA] preferred term [PT]), duration, intensity, and relationship to vaccination of any unsolicited systemic AEs reported in the 30 minutes after vaccination 	
	• Occurrence, time of onset, number of days of occurrence, intensity, action taken, and whether the reaction led to early termination from the study, of solicited (prelisted in the subject's diary card [booklet or electronic device (e-diary)] and electronic case report book [CRB]) injection site reactions occurring up to 7 days after vaccination	
	Note : The diary card may be either a booklet or an electronic device that contains an application to enter the information (e-diary).	
	 Occurrence, time of onset, number of days of occurrence, intensity, action taken, and whether the reaction led to early termination from the study, of solicited (prelisted in the subject's diary card [booklet or e- diary] and CRB) systemic reactions occurring up to 7 days after vaccination 	
· · · · · · · · · · · · · · · · · · ·	·	

	 Occurrence, nature (MedDRA PT), time of onset, duration, intensity, action taken, relationship to vaccination (for systemic AEs only), and whether the event led to early termination from the study, of unsolicited AEs up to Visit 2 after vaccination Occurrence, nature (MedDRA PT), time of onset, duration, seriousness criteria, relationship to vaccination, outcome, and whether the SAE led to early termination from the study, of SAEs, including AESIs, 		
	throughout the trial		
Planned Sample Size:	A total of 188 subjects who participated in the MET54 study are planned to be enrolled.		
Schedule of Study Procedures:	Vaccination		
	All subjects will receive a single dose of MenACYW conjugate vaccine at Visit 1 (D0).		
	Blood sampling		
	All subjects will provide a pre-vaccination blood sample on D0 and a post-vaccination sample at Visit 2 (30 to 44 days after the vaccination at Visit 1).		
	Collection of safety data		
	All subjects will be observed for 30 minutes after vaccination and any unsolicited systemic AEs occurring during that time will be recorded as immediate unsolicited systemic AEs in the CRB.		
	The subject's parent / legally acceptable representative will record information in a diary card (booklet or e-diary) about solicited reactions from D0 to D07 after vaccination and unsolicited AEs from D0 to Visit 2. SAEs will be reported throughout the duration of the trial.		
	• In addition, the subject's parent / legally acceptable representative will be asked to notify the site immediately about potential SAEs at any time during the trial.		
	• Alerts will be sent to the e-diary (if applicable) and staff will contact the subject's parent / legally acceptable representative by telephone on D08 (+2 days) to identify the occurrence of any SAE not yet reported, and to remind them to complete the diary card (booklet or e-diary) up to Visit 2 and to bring it back at Visit 2.		
	• The completed diary card (booklet or e-diary) will be reviewed with the subject's parent / legally acceptable representative at Visit 2.		
Duration of Participation in the Trial:	The duration of each subject's participation in the study will be 30 to 44 days.		
Investigational Product:	MenACYW conjugate vaccine: Meningococcal Polysaccharide (Serogroups A, C, Y, and W) Tetanus Toxoid Conjugate Vaccine (Sanofi Pasteur Inc., Swiftwater, PA, USA)		
Form:	Liquid solution		
Composition:	Each 0.5 milliliter (mL) dose of MenACYW conjugate vaccine is formulated in sodium acetate buffered saline solution to contain the following ingredients:		
· · · · · · · · · · · · · · · · · · ·			

	Meningococcal capsular polysaccharides:	
	Serogroup A 10 micrograms (μg) Serogroup C 10 μg Serogroup Y 10 μg Serogroup W 10 μg	
	Tetanus toxoid protein carrierapproximately 55 µg*	
	* Tetanus toxoid protein quantity is approximate and dependent on the polysaccharide-to-protein ratio for the conjugates used in each formulation.	
Route:	IM	
Batch Number:	To be determined	
Inclusion Criteria:	An individual must fulfill all of the following criteria in order to be eligible for trial enrollment:	
	1) Participated in and completed (attended Visit 2) study MET54	
	 Informed consent form has been signed and dated by the parent(s) or another legally acceptable representative (and by an independent witness, if required by local regulations) 	
	3) Subject and parent/legally acceptable representative are able to attend all scheduled visits and to comply with all trial procedures	
	4) Covered by health insurance where applicable	
Exclusion Criteria: An individual fulfilling any of the following criteria is to be trial enrollment:		
	1) Participation in the 4 weeks preceding the trial vaccination or planned participation during the present trial period in another clinical trial investigating a vaccine, drug, medical device, or medical procedure	
	2) Receipt of any vaccine in the 4 weeks (28 days) preceding the trial vaccination or planned receipt of any vaccine prior to Visit 2 except for influenza vaccination, which may be received at a gap of at least 2 weeks before or after the study vaccines. This exception includes monovalent pandemic influenza vaccines and multivalent influenza vaccines. If the subject is due to receive vaccination(s) recommended for his / her age by the national immunization schedule at the time of the study, the subject will be recommended to complete his/her immunization schedule after Visit 2.	
	3) Previous vaccination against meningococcal disease with either the trial vaccine or another vaccine (i.e., mono- or polyvalent, polysaccharide, or conjugate meningococcal vaccine containing serogroups A, C, Y, or W; or meningococcal B vaccine) with the exception of the single dose of meningococcal vaccine administered as part of study MET54	
	4) Receipt of immune globulins, blood or blood-derived products in the past 3 months	
	5) Known or suspected congenital or acquired immunodeficiency; or receipt of immunosuppressive therapy, such as anti-cancer chemotherapy or radiation therapy, within the preceding 6 months; or long-term systemic corticosteroid therapy (prednisone or equivalent for more than 2 consecutive weeks within the past 3 months)	

- 6) History of meningococcal infection, confirmed either clinically, serologically, or microbiologically
- 7) At high risk for meningococcal infection during the trial (specifically, but not limited to, subjects with persistent complement deficiency, with anatomic or functional asplenia, or subjects traveling to countries with high endemic or epidemic disease)
- 8) Known systemic hypersensitivity to any of the vaccine components, or history of a life-threatening reaction to the vaccine used in the trial or to a vaccine containing any of the same substances
- 9) Verbal report of thrombocytopenia, contraindicating intramuscular vaccination in the Investigator's opinion
- 10) Bleeding disorder, or receipt of anticoagulants in the 3 weeks preceding inclusion, contraindicating intramuscular vaccination
- 11) Personal history of Guillain-Barré syndrome (GBS)
- 12) Personal history of an Arthus-like reaction after vaccination with a tetanus toxoid-containing vaccine
- 13) Chronic illness that, in the opinion of the Investigator, is at a stage where it might interfere with trial conduct or completion
- 14) Moderate or severe acute illness/infection (according to Investigator judgment) on the day of vaccination or febrile illness (temperature ≥ 38.0°C). A prospective subject should not be included in the study until the condition has resolved or the febrile event has subsided
- 15) Receipt of oral or injectable antibiotic therapy within 72 hours prior to the first blood draw.
- 16) Identified as a natural or adopted child of the Investigator or employee with direct involvement in the proposed study

Statistical Methods:

All immunogenicity analyses will be performed on the Per-Protocol Analysis Set (PPAS). Additional immunogenicity analyses will be performed for exploratory purposes on the Full Analysis Set (FAS). All safety analyses will be performed on the Safety Analysis Set (SafAS). All analyses will be based on the overall study population as well as the type of meningococcal vaccine received in MET54 (subjects who received MenACYW conjugate vaccine and subjects who received Nimenrix® 3 years earlier as toddlers).

Immunogenicity

All analyses will be descriptive; no hypotheses will be tested. Descriptive statistics will be provided for the hSBA and rSBA antibody titers against meningococcal serogroups (A, C, Y, and W) and for antibody concentrations against tetanus toxoid contained in MenACYW conjugate vaccine.

In general, categorical variables will be summarized and presented by frequency counts, proportion percentages, and confidence intervals (CIs). The 95% CIs of point estimates will be calculated using the normal approximation for quantitative data and the exact binomial distribution (Clopper-Pearson method) for percentages. For geometric mean titers (GMTs), 95% CIs of point estimates will be calculated using normal approximation assuming they are log-normally distributed.

Reverse cumulative distribution curve (RCDC) figures will be provided for the antibody titers against meningococcal serogroups and the antibody concentrations against tetanus toxoid contained in MenACYW conjugate vaccine.

In summary, descriptive analyses on A, C, Y, and W serogroups will include but not be limited to:

- hSBA and rSBA GMTs and 95% CI
- hSBA and rSBA titer distribution and RCDC
- Percentage of subjects with hSBA titer $\geq 1:4$ and $\geq 1:8$ and 95% CI
- Percentage of subjects with rSBA titer ≥ 1.8 and ≥ 1.128 and 95% CI

Percentage of subjects with hSBA and rSBA titer ≥4-fold rise from prevaccination to post-vaccination, and 95% CI

 Percentage of subjects with hSBA and rSBA vaccine seroresponse* rate and 95% CI

*hSBA vaccine seroresponse (definition proposed by the Center for Biologics Evaluation and Research [CBER] in 2016) for serogroups A, C, Y, and W is defined as:

- For a subject with a pre-vaccination titer < 1:8, the post-vaccination titer must be ≥ 1:16.
- For a subject with a pre-vaccination titer ≥ 1:8, the post-vaccination titer must be at least 4-fold greater than the pre-vaccination titer.

hSBA vaccine seroresponse (definition used in study MET54) for serogroups A, C, Y, and W is defined as:

- For a subject with a pre-vaccination titer < 1:8, the post-vaccination titer must be ≥ 1:8.
- For a subject with a pre-vaccination titer ≥ 1:8, the post-vaccination titer must be at least 4-fold greater than the pre-vaccination titer

rSBA vaccine seroresponse is defined as:

• a post-vaccination rSBA titer \geq 1:32 for subjects with pre-vaccination rSBA titer < 1:8,

or

• a post-vaccination titer ≥ 4 times the pre-vaccination titer for subjects with pre-vaccination rSBA titer ≥ 1:8.

In summary, descriptive analyses on anti-tetanus antibody concentrations will include but not be limited to:

- Geometric mean concentrations (GMCs) and 95% CI
- The percentage of subjects with antibody concentrations to tetanus toxoid ≥ 0.01 international units (IU)/mL and ≥ 0.1 IU/mL and 95% CI

Data from MET54 and MET62 will also be combined and paired to evaluate antibody persistence and overall trends over 3 years.

Safety

Safety results will be described for subjects in the study. The main parameters for the safety endpoints will be described by 95% CIs (based on the Clopper-Pearson method).

Calculation of Sample Size:

This is an exploratory study with no hypothesis-driven primary objectives. All available subjects who participated in and completed the MET54 study and received either MenACYW conjugate vaccine or Nimenrix® vaccine, as a part of the study, will be enrolled.

Table of Study Procedures

Phase III Study, 2 Visits, 1 Vaccination, 2 Blood Samples, 1 Telephone Call, 30 Days Duration per Subject

Visit/Contact	Visit 1	Telephone Call 1	Visit 2
Trial timelines (days)	D0	D08	D30
Time windows (days)		+2 days	+14 days
Informed consent	X		
Inclusion/exclusion criteria	X		
Collection of demographic data	X		
Medical history	X		
Physical examination*	X		
Review of temporary contraindications for blood sampling [†]			X
Allocation of subject number	X		
Blood sampling (BL), 5 mL [‡]	BL1		BL2
Vaccination§	X		
Immediate surveillance (30 minutes)	X		
Diary card (booklet or e-diary) provided	X		
Telephone call		X**	
Recording of solicited injection site & systemic reactions	D0 to D07		
Recording of unsolicited AEs		D0 to Visit 2	•
Reporting of SAEs (including AESIs) ^{††}	AEs (including AESIs) ^{††} To be reported throughout the study p		study period
Diary card (booklet or e-diary) reviewed and collected			X
Collection of reportable concomitant medications	X		X
Trial termination record			X

^{*}Temperature needs to be measured and recorded in source documents.

[†] Should a subject receive oral or injectable antibiotic therapy within 3 days prior to the second blood draw, the Investigator will postpone that blood draw until it has been 3 days since the subject last received oral or injectable antibiotic therapy. Postponement must still be within the timeframe for blood draw (30 to 44 days after vaccination at D0). If postponement would result in the sample collection falling outside of the 30 to 44 day timeframe, the blood sample should be collected without postponement and it should be documented that the sample was taken less than 3 days after stopping antibiotic treatment.

[‡] Blood sample at Visit 1 will be drawn before administration of vaccine

[§] Subjects will receive 1 dose of MenACYW conjugate vaccine

^{**} This call is made 8 to 10 days after the vaccination at Visit 1. If D08 (+2 days) falls on a weekend or holiday, the telephone call may be made on the following business day. During this telephone call, the staff will find out whether the subject experienced any SAE, including AESIs, not yet reported, and will remind the subject's parent / legally acceptable representative to continue using the diary card (booklet or e-diary) up to Visit 2, to bring the diary card (booklet or e-diary) to the study center at Visit 2, and confirm the date and time of Visit 2. Additionally, an alert may be sent to the e-diary (as applicable) to remind the subject's parent / legally acceptable representative to report any SAEs, including AESIs, not yet reported and to continue to use the e-diary up to Visit 2, to bring the e-diary to the study center at Visit 2, and confirm the date and time of Visit 2.

^{††} AESIs will be collected throughout the trial as SAEs to ensure that the events are communicated to the Sponsor in an expedited manner and followed up until the end of the follow-up period or resolution, as per the assigned causality.

List of Abbreviations

μg microgram(s)
AE adverse event

AESI adverse event of special interest

AR adverse reaction

BL blood sampling/sample

CBER Center for Biologics Evaluation and Research

CDM Clinical Data Management

CFU colony-forming unit

CHMP Committee for Medicinal Products for Human Use

CI confidence interval

CQA Clinical Quality Assessment
CRA Clinical Research Associate

CRB (electronic) case report book (all the case report forms for a subject)

CRF (electronic) case report form
CTA clinical trial agreement
CTL Clinical Team Leader

D day

EDC electronic data capture
ECL electrochemiluminescent
EMA European Medicines Agency

FAS full analysis set

FVFS first visit, first subject
FVLS first visit, last subject
GBS Guillain-Barré syndrome
GCI Global Clinical Immunology

GCP Good Clinical Practice

GMC geometric mean concentration

GMT geometric mean titer

GPV Global PharmacoVigilance

hSBA serum bactericidal assay using human complement

IATA International Air Transport Association

ICF informed consent form

ICH International Council for Harmonisation

IEC Independent Ethics Committee

IgG immunoglobulin G

IM intramuscular(ly)

IMD invasive meningococcal disease

IME important medical event IOM Institute of Medicine

IRB Institutional Review Board

IRT interactive response technology

ITP idiopathic thrombocytopenic purpura

IU international units

LLOQ lower limit of quantitation

LLT lowest level term

MedDRA Medical Dictionary for Regulatory Activities

mL milliliter

NSAID non-steroidal anti-inflammatory drug

PPAS per-protocol analysis set

PS polysaccharide
PT preferred term
PV Pharmacovigilance

RCDC reverse cumulative distribution curve

RMO Responsible Medical Officer

rSBA serum bactericidal assay using rabbit complement

SAE serious adverse event
SafAS safety analysis set
SAP statistical analysis plan
SMT Safety Management Team

TMF Trial Master File

ULOQ upper limit of quantitation

UN United Nations

WHO World Health Organization

1 Introduction

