1.2.1.2 Study MET54 (Phase II)

MET54 was a Phase II, randomized, open-label, active-controlled, multi-center study conducted in Europe (Finland). This study evaluated the immunogenicity and safety profile of a single dose of MenACYW conjugate vaccine when given alone in healthy, meningococcal-vaccine naïve toddlers compared to that of the licensed vaccine Nimenrix[®]. A total of 188 meningococcal vaccine naïve subjects aged 12 to 23 months on the day of enrollment were randomized to 1 of 2 groups. Group 1 received a single dose of MenACYW conjugate vaccine and Group 2 received a single dose of Nimenrix[®].

Immunogenicity

Antibody responses to the antigens (serogroups A, C, Y, and W) were evaluated by serum bactericidal assay using human complement (hSBA) and baby rabbit complement (rSBA). MenACYW conjugate vaccine immune responses evaluated by hSBA and rSBA were generally comparable to Nimenrix[®] immune responses with some variation by serogroup:

hSBA

Most subjects in both groups had hSBA titers ≥ 1:8 at D30: the percentages after MenACYW conjugate vaccine for serogroups A, Y, and W (ranging from 97.8% [89/91] to 98.9% [90/91])

were comparable to those after Nimenrix® (ranging from 91.9% [79/86] to 100.0% [86/86]). The percentage of subjects with hSBA titers ≥ 1.8 for serogroup C was higher after MenACYW conjugate vaccine (100.0% [91/91]) than after Nimenrix® (89.5% [77/86]). At D30, most subjects in both groups demonstrated an hSBA vaccine seroresponse. The percentage of subjects with an hSBA vaccine seroresponse for serogroups A, Y, and W was comparable in both groups (ranging from 96.7% [87/90] to 98.9% [90/91] after MenACYW conjugate vaccine and from 91.9% [79/86] to 98.8% [85/86] after Nimenrix®). The percentage of subjects with an hSBA vaccine seroresponse for serogroup C was higher after MenACYW conjugate vaccine (100.0% [91/91]) than after Nimenrix® (86.0% [74/86]).

rSBA

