5.2 Enrollment and Retention of Study Population

5.2.1 Recruitment Procedures

Before the start of the trial, the Investigator and / or study staff will contact the parents / legally acceptable representatives of subjects who had previously participated in study MET54 and invite them to participate in the study. The site will ensure that any advertisements used to recruit subjects (e.g. letters, pamphlets, and posters) are submitted to Sanofi Pasteur for review prior to submission to the IEC/ IRB for approval.

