5.2.4 Inclusion Criteria

An individual must fulfill *all* of the following criteria to be eligible for study enrollment:

- 1) Participated in and completed (attended Visit 2) study MET54
- 2) Informed consent form has been signed and dated by the parent(s) or another legally acceptable representative (and by an independent witness, if required by local regulations)
- 3) Subject and parent/legally acceptable representative are able to attend all scheduled visits and to comply with all trial procedures
- 4) Covered by health insurance where applicable

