5.2.5 Exclusion Criteria

An individual fulfilling *any* of the following criteria is to be excluded from study enrollment:

- 1) Participation in the 4 weeks preceding the trial vaccination or planned participation during the present trial period in another clinical trial investigating a vaccine, drug, medical device, or medical procedure
- 2) Receipt of any vaccine in the 4 weeks (28 days) preceding the trial vaccination or planned receipt of any vaccine prior to Visit 2 except for influenza vaccination, which may be received at a gap of at least 2 weeks before or after the study vaccines. This exception includes monovalent pandemic influenza vaccines and multivalent influenza vaccines. If the subject is due to receive vaccination(s) recommended for his / her age by the national

- immunization schedule at the time of the study, the subject will be recommended to complete his/her immunization schedule after Visit 2.
- 3) Previous vaccination against meningococcal disease with either the trial vaccine or another vaccine (i.e., mono- or polyvalent, polysaccharide, or conjugate meningococcal vaccine containing serogroups A, C, Y, or W; or meningococcal B vaccine) with the exception of the single dose of meningococcal vaccine administered as part of study MET54
- 4) Receipt of immune globulins, blood or blood-derived products in the past 3 months
- 5) Known or suspected congenital or acquired immunodeficiency; or receipt of immunosuppressive therapy, such as anti-cancer chemotherapy or radiation therapy, within the preceding 6 months; or long-term systemic corticosteroid therapy (prednisone or equivalent for more than 2 consecutive weeks within the past 3 months)
- 6) History of meningococcal infection, confirmed either clinically, serologically, or microbiologically
- 7) At high risk for meningococcal infection during the trial (specifically, but not limited to, subjects with persistent complement deficiency, with anatomic or functional asplenia, or subjects traveling to countries with high endemic or epidemic disease)
- 8) Known systemic hypersensitivity to any of the vaccine components, or history of a lifethreatening reaction to the vaccine used in the trial or to a vaccine containing any of the same substances^a
- 9) Verbal report of thrombocytopenia, contraindicating intramuscular vaccination in the Investigator's opinion

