12.5 Determination of Sample Size and Power Calculation

This is an exploratory study with no hypothesis-driven primary objectives. All available subjects who participated in and completed the MET54 study and received either MenACYW conjugate vaccine or Nimenrix® vaccine, as a part of the study, will be enrolled.

13 Ethical and Legal Issues and Investigator / Sponsor Responsibilities

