## 5.5 Determination of Sample Size and Power Calculation

No sample size calculations were performed. This is an exploratory study with no hypothesis-driven primary objectives. All available subjects who participated in and completed the MET54 study and received either MenACYW conjugate vaccine or Nimenrix® vaccine, as a part of the study, were to be enrolled.

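### Is a planned sample size of 188 wrong because it equals everyone randomized in MET54?

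*Protocol*

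**What the plan says.** The Planned Sample Size entry in the protocol synopsis reads "A total of 188 subjects who participated in the MET54 study are planned to be enrolled". Protocol 1.2.1.2, describing the parent study, says "A total of 188 meningococcal vaccine naïve subjects aged 12 to 23 months on the day of enrollment were randomized" to its two groups.

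MET62 draws on that cohort alone. Under Protocol 5.2.1 sites contact the families of "subjects who had previously participated in study MET54 and invite them to participate in the study". Further conditions then apply:

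- Inclusion criterion 1 (Protocol 5.2.4): "Participated in and completed (attended Visit 2) study MET54". The same section requires new signed consent.
- Timing (synopsis and Protocol 5.1.1): eligibility is for "Subjects who were vaccinated 3 years (± 45 days) earlier at 12 to 23 months of age in study MET54".
- Exclusion criterion 3 (Protocol 5.2.5): "Previous vaccination against meningococcal disease with either the trial vaccine or another vaccine", apart from the one MET54 dose.

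The sample size sections give a rule and no number. Protocol 12.5 enrolls "All available subjects who participated in and completed the MET54 study" and received either vaccine, and calls the study exploratory. The synopsis entry Calculation of Sample Size carries the same rule. SAP 5.5 repeats it and adds "No sample size calculations were performed".

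**The concern.** A fixed total of 188 reads like an expected yield, yet it is the whole randomized cohort of a study vaccinated three years earlier. Reaching it would need every child to have completed MET54, every family to return and consent again, and almost no child to be ineligible. Neither document allows for any loss, and the synopsis figure is counted from participants whereas Protocol 12.5 and SAP 5.5 speak of completers.

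In a descriptive study the sample size governs one statistical property, the width of the intervals, and these are reported by MET54 vaccine group as well as overall. If 188 is the best case, a reader or ethics committee who takes it as the expected size will expect somewhat narrower intervals than the trial delivers. The natural remedy would be to write *up to 188* and add the MET54 completer count and an expected range per group.

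**Working it through.** **Inputs from the documents**

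- Planned enrollment in MET62: 188 (Protocol synopsis).
- Randomized in MET54: 188 (Protocol 1.2.1.2).
- Day 30 denominators reported for MET54: 91 and 86 (Protocol 1.2.1.2).
- Hypotheses, power, margin: none (Protocol 12.1.1.1, Protocol 12.5, SAP 5.5).
- Interval for a percentage: exact Clopper-Pearson, 95% (Protocol 12.1.1.2, SAP 5.1.1.2.1).

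**Step 1: where 188 comes from**

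188 randomized × 100% completion × 100% re-consent × 100% eligibility = 188. The figure reproduces exactly as a head count, so there is no arithmetic error.

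The alternative 91 + 86 = 177 (177/188 = 94.1%) does not give 188. The protocol does not say which analysis set those denominators belong to, so 177 is not a completer count and does not show that 188 was out of reach.

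**Step 2: is it a ceiling?**

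Yes. There is no other source of subjects, and each condition can only reduce the number. The 100% eligibility term is slightly too strict, because SAP 5.2.4 counts a subject as enrolled once a case report form exists, so a child later found ineligible could still count. That does not raise the ceiling.

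**Step 3: what a shortfall does to precision**

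The documents give no return rate and no MET54 completer count, so the enrolled shares below are assumptions, as are equal groups and an observed proportion near 50%. That proportion gives the widest interval. The Clopper-Pearson limits for x out of n are the 2.5% quantile of Beta(x, n − x + 1) and the 97.5% quantile of Beta(x + 1, n − x).

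| Share of 188 | Total | Per group | x/n used | 95% CI (%) | Width (points) |
|---|---|---|---|---|---|
| 100% | 188 | 94 | 47/94 | 39.5–60.5 | 21.0 |
| 90% | 169 | 85 | 42/85 | 38.4–60.5 | 22.1 |
| 80% | 150 | 75 | 38/75 | 38.9–62.4 | 23.6 |
| 70% | 132 | 66 | 33/66 | 37.4–62.6 | 25.1 |
| 60% | 113 | 56 | 28/56 | 36.3–63.7 | 27.3 |
| 50% | 94 | 47 | 24/47 | 36.1–65.9 | 29.9 |

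Totals and group sizes are rounded; widths come from unrounded limits.

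The MET54 day 30 percentages quoted in Protocol 1.2.1.2 run from 86.0% to 100%. Near 95% the intervals are about half as wide: 89/94 gives 88.0–98.3 (10.2 points) and 71/75 gives 86.9–98.5 (11.6 points). Moving from full to 80% return then costs 1.4 points, against 2.6 points in the 50% case. Three-year persistence could lie nearer 50%; the documents give no figure.

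The enrolled number is also not the denominator for these intervals. Under SAP 5.2.5 immunogenicity uses the per-protocol set and persistence uses the full analysis set for persistence. The table therefore illustrates scale and does not predict the trial's precision.

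**Step 4: does anything in the plan use 188?**

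No. No test, power statement, precision target, stopping rule or enrollment rule refers to it. Every estimate and interval is computed on the analysis set obtained.

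**The case for a change.** The strongest case for a change is that the defect is certain and the repair is one line. A flat total does not announce itself as a maximum, it is the only enrollment figure in either document, and it sits beside a rule that is conditional and counts completers. Where the whole output is estimates with intervals, in young children asked for two blood samples and an investigational booster, a realistic size is fair to ask for.

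Part of this stands. Writing *up to 188* would be clearer and would match the all-available rule more closely.

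The rest does not carry. The synopsis gives the conditional rule as well as the number, so a reader of the synopsis alone is told that enrollment means whoever is available among the completers. Planning to approach the whole cohort is a reasonable meaning of *planned*, and nowhere is 188 described as an expected return. Protocol 12.5 and SAP 5.5 contain no number to correct. SAP 5.5 is written in the past tense, which suggests that an expected range added there would come too late to inform anyone.

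**Conclusion.** The concern does not call for a change. It is true that 188 is the full MET54 cohort and therefore an upper limit. That is a loose label on one synopsis line; the figure itself is correctly counted, and the rule that governs enrollment is stated in three places.

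Its size is small. Under the assumptions of equal groups and an observed 50%, return of 80% instead of 100% widens a per-group interval from 21.0 to 23.6 points. The documents do not say what return to expect, so they show 188 to be a maximum without showing how far short enrollment would fall. Rewording the line would leave conduct, analysis sets, estimates, intervals and conclusions as they are.

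The conclusion rests on the study remaining purely descriptive. If a hypothesis test or a precision target had been tied to 188, a realistic enrolled number would have been needed.
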